8.6 Adverse Event/ Unanticipated Problems

8.6.1 Definitions

8.6.1.1 Adverse Event (AE)

For the purposes of this study, we know of no adverse events related to the clinical interventions in the study. Adverse events would therefore include protocol violations and/or breaches of confidentiality. Breaches of confidentiality are unlikely given the above procedures in place. Protocol violations will be identified using audits and feedback of patient records to ensure protocols are being followed and any complaints from patients. Any instances of protocol violation or breach of confidentiality will be reported to the IRB and to PCORI.

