1.4 Research Risks & Benefits

1.4.1 Risk of Investigational Device

The only known risks are allergies to silver and short-term (3-7 day) irritation from dripping on gingiva or epithelium. However oral health professionals working in this study will be trained on the proper techniques to avoid risks. All students with a silver allergy will be excluded from participating. The application of silver diamine fluoride may discolor any cavities resulting in a brown or black color. This color change indicates that the cavity has stopped growing. If accidental skin contact occurs it can cause a temporary light brown staining to the lips, cheeks, or permanent staining to clothing. For stain removal to the skin, soap and water are applied immediately. The same procedure is applied for cleaning clothes.

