3.4 Primary Safety Endpoints

The care provided is usual and customary care, not high-risk. The only risk about which we are aware is a toothache. Our history suggests that this occurs in approximately 1 in 2000 children. In our experience, this occurrence is far less than the percentage of children with tooth aches prior to initiation of prevention (approximately 5 in 100 children).

4 Participant Selection, Enrollment, and Withdrawal

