8.5 Expected Risks

There are no expected risks associated with the clinical interventions proposed in this study. The only risk would be a data breach. The only possibility for a data breach would be the loss or theft of the tablet computers (Apple iPads) used for data collection. However, data is typically synced with NESS before the data collector leaves the school.

The iPads are transported by our clinical staff in a locked backpack to and from treatment locations. The iPads are locked each night in a closet on the 8th floor at NYUCD.

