8.9.3 Adverse Event Reporting of Non-IND Studies

SAEs that are unanticipated, serious, and possibly related to the study intervention will be reported to the IRB and PCORI in accordance with requirements.

- Unexpected fatal or life-threatening AEs related to the intervention will be reported to the PCORI Project Manager within 3 days of the investigator becoming aware of the event. Other serious and unexpected AEs related to the intervention will be reported within 7 days.
- Anticipated or unrelated SAEs will be handled in a less urgent manner but will be reported to the IRB in accordance with their requirements and will be reported to PCORI on an annual basis.
- All other AEs documented during the course of the trial will be reported to PCORI on an annual basis by way of inclusion in the annual report and in the annual AE/DSMP summary which will be provided to PCORI.

We note that no clinical adverse events are expected.

- 8.9.4 Adverse Event Reporting of Investigation New Drug (IND) Studies Not applicable.
- 8.9.5 Events of Special Interest (if applicable) Not applicable.

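### Section 8.6.1.1 names only administrative events as adverse events, contradicting the clinical risks in 1.4.1 and 3.4, and non-serious clinical events are nowhere defined

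*Combined protocol and SAP*

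**What the plan says.** The adverse event definition is in 8.6.1.1. Its premise is that "we know of no adverse events related to the clinical interventions in the study", and its conclusion is that "Adverse events would therefore include protocol violations and/or breaches of confidentiality". Two other sections of the safety monitoring plan take the same line. Section 8.5 states: "There are no expected risks associated with the clinical interventions proposed in this study". Section 8.9.3 closes with: "We note that no clinical adverse events are expected".

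Two earlier sections say otherwise. Section 1.4.1 states: "The only known risks are allergies to silver and short-term (3-7 day) irritation from dripping on gingiva or epithelium". It goes on to describe dark discoloration of treated cavities and temporary staining of skin. Section 3.4, under the heading for primary safety endpoints, states: "The only risk about which we are aware is a toothache". It gives a rate, "Our history suggests that this occurs in approximately 1 in 2000 children", and compares it with the rate before prevention, "approximately 5 in 100 children".

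The rest of Section 8 is written in clinical terms. Section 8.6.1.3 defines serious adverse events by the usual seriousness criteria. Section 8.7 has the investigator ask about adverse events at each visit. Sections 8.8.1 and 8.8.3 give attribution and severity scales, and 8.9.3 sends non-serious events to the funder annually. Section 8.14 requires the annual report to address whether adverse event rates agree with what was assumed beforehand.

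**The concern.** A definition of adverse events should tell staff which clinical occurrences to write down. This one names none, and it rests on a premise that 1.4.1 and 3.4 contradict. The events left without a definition are the non-serious ones that the protocol itself foresees: ordinary toothache, soft-tissue irritation, staining and mild allergic reaction.

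Several controls depend on these events being recorded in the same way everywhere. They are the annual comparison with pre-study assumptions (8.14), the judgement of expectedness against risk information already described (8.8.2), and the halting and stopping provisions, which refer to reactions, event frequency and adverse effects (8.10, 8.13). Clinicians are unblinded and work in teams that deliver only one type of prevention (6.5.2). If teams settle the ambiguity differently, the difference in recording follows treatment arm and could be mistaken for, or could hide, a difference in safety.

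**Working it through.** The plan states no safety sample size or power to reproduce, so the main check is textual. The arithmetic afterwards only gives scale.

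**1. What each section says about clinical risk**

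| Section | Position |
|---|---|
| 1.4.1 | Silver allergy, irritation lasting 3 to 7 days, staining |
| 3.4 | Toothache, with a rate |
| 8.5 | No clinical risk; a data breach is the only risk |
| 8.6.1.1 | No intervention-related adverse events known; administrative events named |
| 8.9.3 | No clinical adverse events expected |

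The last three rows cannot stand alongside the first two. Sections 1.4.1 and 3.4 also disagree with each other, since each gives a different risk as the only one known.

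**2. Whether another section supplies the definition**

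- 8.6.1.3 covers serious events only. Ordinary toothache, brief irritation and staining would not normally qualify.
- 8.6.1.2 and 8.9.2 cover unanticipated problems, whereas these events were named in advance.
- 8.7, 8.8.1 and 8.8.3 say how to ask about, attribute and grade an adverse event, but not what counts as one.
- 8.9.3 says how documented events are reported, but not which to document.

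No section fills the gap.

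**3. Whether a comparison by arm is planned.** Section 7 contains no safety analysis. Section 8.14 limits study report tables to data pooled over groups.

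**4. Expected toothaches.** Inputs: 14,100 children in 60 randomized schools and about 3,760 in the 16 once-yearly schools (7.1); rates of 1 in 2000 and 5 in 100 (3.4), treated as per child because no time base is given.

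- Randomized schools: 14,100 / 2000 = 7.05, or about 3.5 per arm with equal arms of 7,050.
- Pre-prevention rate: 14,100 × 0.05 = 705, or about 353 per arm.
- All 76 schools: 17,860 / 2000 = 8.9, and 17,860 × 0.05 = 893.

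**5. What complete recording could detect.** For two proportions at two-sided 0.05, power = Φ{[|p2 − p1|√n − 1.96√(2p̄(1 − p̄))] / √[p1(1 − p1) + p2(1 − p2)]}. Here p1 = 1/2000, p2 is a multiple of p1, p̄ is their mean, and n = 7,050 / design effect. The plan's design effect for caries arrest reproduces: 1 + (235 − 1) × 0.10 = 24.4. No intraclass correlation is given for toothache, so a range is shown.

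| Clustering | Design effect | n per arm | Twofold | Fivefold | Tenfold |
|---|---|---|---|---|---|
| None | 1 | 7,050 | 19% | 87% | >99% |
| ICC 0.01 (assumed) | 3.34 | 2,111 | 9% | 39% | 80% |
| ICC 0.10 (caries arrest value) | 24.4 | 289 | 4% | 9% | 18% |

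With no clustering, 80% power for a doubling would need about 47,057 children per arm. The approximation is rough with so few events, especially in the last row.

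**The case against.** The strongest reply is that 8.6.1.1 says adverse events include administrative ones, not that they consist only of them, and that the safety plan read as a whole is clinical. Attribution by timing, abatement and re-challenge, and grading by symptoms and daily activities, make sense only for clinical events. Section 8.7 even sets a follow-up window for non-serious events.

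Much of this stands, and it rules out several stronger readings that a reader might infer:

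- **That clinical events are excluded by definition.** The wording is not exclusive.
- **That no valid safety comparison is possible, or that safety would rest on no data.** Serious clinical events, including a serious allergic reaction, are captured under 8.6.1.3 and could be compared by arm.
- **That staff would record nothing clinical and the annual check would be empty.** No section says how staff would resolve the conflict.
- **That toothache is a fully specified endpoint.** Section 3.4 names it and gives background rates, but no case definition, timing or method of measurement.

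It is also fair to say that better recording would not give a precise comparison of toothache, as the power table shows. The limit on tables in 8.14 may be meant only for reports during the trial.

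The reply does not remove the contradiction between sections. Nor does a non-exclusive verb supply the missing definition: a team that follows 8.6.1.1 literally and a team that follows 8.8 could both claim compliance.

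**Conclusion.** The concern holds as an internal contradiction with a practical consequence. Sections 8.5, 8.6.1.1 and 8.9.3 deny clinical risks that 1.4.1 and 3.4 name, and no section defines a non-serious clinical adverse event. Toothache, irritation, staining and non-serious allergic reactions may be recorded inconsistently or under-ascertained. This weakens the annual check in 8.14 and any between-arm comparison of these events. Ascertainment of serious events is not affected.

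The size of any under-recording cannot be derived from the documents. For scale, the two rates in 3.4 differ a hundredfold (705 / 7.05), so the annual check could reveal a large departure from 1 in 2000, but only if toothaches are recorded. The counts assume a per-child rate with no time base and equal arms; the power figures also assume the clustering values shown.

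The contradiction is certain from the text. How far it would affect recording in practice is not known.

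**What to change.** - In 8.6.1.1, define an adverse event as any untoward medical or oral event after enrolment, whether or not judged related.
- List the events already named in 1.4.1 and 3.4 as solicited events at the existing visit inquiry: toothache, gingival or mucosal irritation, allergic reaction and staining. Give toothache a time base so that the 8.14 check has a usable reference rate.
- Keep protocol violations and privacy breaches as a separate category with their own reporting line.
- Reconcile 8.5, 8.6.1.1 and 8.9.3 with 1.4.1 and 3.4.
- Add to Section 7 a final tabulation of adverse events by arm, and state in 8.14 that the limit to pooled tables does not apply to it.

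The cost is protocol wording and a short checklist in the existing electronic record; no treatment changes. More minor events will be reported. Irritation lasting 3 to 7 days will depend on recall, because children are seen once or twice a year. About 7 expected toothaches will reveal only large differences, so the by-arm table should be presented as descriptive.

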8.6.1.2 Unanticipated Problems (UP)

Unanticipated problems will be recorded in the data collection system throughout the study.

8.6.1.3 Serious Adverse Event (SAE)

A serious adverse event (SAE) is one that meets one or more of the following criteria:

- Results in death
- Is life-threatening (places the subject at immediate risk of death from the event as it occurred)
- Results in inpatient hospitalization or prolongation of existing hospitalization
- Results in a persistent or significant disability or incapacity
- Results in a congenital anomaly or birth defect

An important medical event that may not result in death, be life threatening, or require hospitalization may be considered an SAE when, based upon appropriate medical judgment, the event may jeopardize the subject and may require medical or surgical intervention to prevent one of the outcomes listed in this definition.

8.7 Time Period and Frequency for Event Assessment and Follow-Up

The PI will record all reportable events with start dates occurring any time after informed consent is obtained until 7 (for non-serious AEs) or 30 days (for SAEs) after the last day of study participation. At each study visit, the investigator will inquire about the occurrence of AE/SAEs since the last visit. Events will be followed for outcome information until resolution or stabilization.

8.8 Characteristics of an Adverse Event

8.8.1 Relationship to Study Intervention

To assess relationship of an event to study intervention, the following guidelines are used:

- 1. Related (Possible, Probable, Definite)
 - a. The event is known to occur with the study intervention.
 - b. There is a temporal relationship between the intervention and event onset.
 - c. The event abates when the intervention is discontinued.
 - d. The event reappears upon a re-challenge with the intervention.
- 2. Not Related (Unlikely, Not Related)
 - a. There is no temporal relationship between the intervention and event onset.

b. An alternate etiology has been established.

8.8.2 Expectedness of SAEs

The Study PIs will be responsible for determining whether an SAE is expected or unexpected. An adverse event will be considered unexpected if the nature, severity, or frequency of the event is not consistent with the risk information previously described for the intervention. No SAEs are expected for clinical interventions in this study.

8.8.3 Severity of Event

The following scale will be used to grade adverse events:

- 1. Mild: no intervention required; no impact on activities of daily living (ADL)
- 2. Moderate: minimal, local, or non-invasive intervention indicated; moderate impact on ADL
- 3. Severe: significant symptoms requiring invasive intervention; subject seeks medical attention, needs major assistance with ADL

8.9 Reporting Procedures

8.9.1 Reporting for Multi-Center Trials Not applicable.

8.9.2 Unanticipated Problem Reporting

Incidents or events that meet the Office of Human Research Protections (OHRP) criteria for unanticipated problems will result in completing an unanticipated problem report form. The following information will be reported when reporting an adverse event, or any other incident, experience, or outcome as an unanticipated problem to the IRB:

- Appropriate identifying information for the research protocol (title, investigator's name, and the IRB project number);
- A detailed description of the adverse event, incident, experience, or outcome;
- An explanation of the basis for determining that the adverse event, incident, experience, or outcome represents an unanticipated problem;
- A description of any changes to the protocol or other corrective actions that have been taken or are proposed in response to the unanticipated problem.

To satisfy the requirement for prompt reporting, unanticipated problems will be reported using the following timeline:

 Unanticipated problems that are serious adverse events will be reported to the IRB and PCORI within 7 days of the investigator becoming aware of the event. Any other unanticipated problem will be reported to the IRB and PCORI within 14 days of the investigator becoming aware of the problem.

8.9.3 Adverse Event Reporting of Non-IND Studies

SAEs that are unanticipated, serious, and possibly related to the study intervention will be reported to the IRB and PCORI in accordance with requirements.

- Unexpected fatal or life-threatening AEs related to the intervention will be reported to the PCORI Project Manager within 3 days of the investigator becoming aware of the event. Other serious and unexpected AEs related to the intervention will be reported within 7 days.
- Anticipated or unrelated SAEs will be handled in a less urgent manner but will be reported to the IRB in accordance with their requirements and will be reported to PCORI on an annual basis.
- All other AEs documented during the course of the trial will be reported to PCORI on an annual basis by way of inclusion in the annual report and in the annual AE/DSMP summary which will be provided to PCORI.

We note that no clinical adverse events are expected.

- 8.9.4 Adverse Event Reporting of Investigation New Drug (IND) Studies Not applicable.
- 8.9.5 Events of Special Interest (if applicable) Not applicable.

8.9.6 Reporting of Pregnancy

Not applicable.

8.10 Halting Rules

Given the 25-year history of the study PIs, we know of no safety issues that would prompt suspension of enrollment or the interventions. However, if we encounter serious, unexpected, and related AEs, the PIs, PCORI, and the IRB would confer to determine whether findings might trigger a safety review based on the number of overall SAEs, the occurrence frequency of the type of SAE, severe AEs/reactions, or increased frequency of events.

8.11 Quality Control and Quality Assurance

Each year of the study, student rosters in participating schools will be requested from the NYC Department of Education, which will include student unique identification numbers, names, addresses, and socio-demographic information.

At the end of each clinic day, the clinical lead in each treatment location will synchronize Apple iPads, used to collect data, with NESS to securely upload examination and clinical data to electronic dental records. Records will then be checked to verify successful transmission, and then erased from each Apple iPad. Transmitted data will include unique identifiers of study participants, demographic information, and examination and care data.

Congruence of unique identifier with demographics (for returning students), as well as in/out of range includes: date of birth with grade, presence/absence and number and type of teeth, increasing occurrence of permanent teeth and decreasing occurrence of primary teeth, and

logic errors (e.g.: change from decay to sound). Records with apparent errors will be set aside for hand check. If errors cannot be rectified, a child's data for a given visit will be excluded from the analysis.

If metrics are beyond established control limits, the CRA will contact the performance site. We will determine if there is special or to determine the cause and see if and how we can assist the performance site.

As indicated in the Research Plan, reports will be generated by the BEDAC and provided to the Co-Pls and Patient and Stakeholder Partners.

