6.1.6 Examination and Diagnosis

Each program will use password-protected Apple iPads with electronic dental records pre-populated with demographic information of all students with informed consent. Student lists on the Apple iPads will be used to: collect students during the care delivery days; record clinical findings and care delivered; and generate take home forms (see below). On the scheduled care days, we will provide a gentle toothbrush cleaning, oral hygiene instruction, a toothbrush and fluoridated toothpaste. We will also carry out an examination and provide preventive care.

The examination will include a soft tissue inspection and an assessment of all primary and permanent teeth to determine the presence/ absence of decay (active or arrested), missing, filled, or sealed surfaces on all teeth.

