6.5.2 Blinding

As a pragmatic trial, this is non-blinded for the participants. Neither schools, nor teachers, nor students, nor clinicians will be blinded. Clinicians will work in teams that only provide either simple or complex prevention. The analysts will be blinded as to the care provided to students in a particular school.

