7.3 Subject Population for Analysis

For study outcomes, participants will be analyzed using intent to treat. All participants will be analyzed as randomized in the original randomization, regardless of whether or not they received an intervention.

For dental-related service use and costs, all New York City elementary school-age children enrolled in Medicaid will be analyzed using intent-to-treat.

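### Section 8.11 drops a child's whole visit for one unresolved decay-to-sound change, so exclusion depends on recorded decay and is neither reported by arm nor tested in a sensitivity analysis

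*Combined protocol and SAP*

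**What the plan says.** Section 8.11 (Quality Control and Quality Assurance) lists the edit checks on uploaded records. Besides agreement of identifier and demographics for returning students, they cover "date of birth with grade, presence/absence and number and type of teeth, increasing occurrence of permanent teeth and decreasing occurrence of primary teeth". The list ends with "logic errors (e.g.: change from decay to sound). Records with apparent errors will be set aside for hand check". The consequence of a failed check is the same for all of them: "If errors cannot be rectified, a child's data for a given visit will be excluded from the analysis".

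The examination in 6.1.6 records "decay (active or arrested), missing, filled, or sealed surfaces on all teeth", so the decay-to-sound check acts on the outcome variable itself.

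On blinding, 6.5.2 states: "Neither schools, nor teachers, nor students, nor clinicians will be blinded". It adds: "Clinicians will work in teams that only provide either simple or complex prevention". Only the analysts are masked.

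Section 7.2 handles tooth turnover tooth by tooth: shed primary teeth and newly erupted permanent teeth drop out of the interval concerned, and the child stays in.

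The documents do not say what counts as rectified, which of two conflicting visits is dropped, or whether the hand checker is masked to arm. They give no expected frequency of these exclusions, no tabulation by arm, no missing-data method and no sensitivity analysis.

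**The concern.** An edit check that deletes data because of the value of the outcome is a selection rule. Here one inconsistent surface removes every tooth examined at that visit. The flag requires decay at an earlier visit, so the visits at risk belong to children with recorded disease, and more recorded disease means more chances to be flagged.

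The GEE analysis of new caries in 7.2 has no provision for missingness that depends on outcome history, and unweighted GEE is not generally valid in that case. New caries is also counted by interval, so a lost visit affects both the interval it closes and the one it opens.

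If flags, or failures to resolve them, are more frequent in one arm, part of the arm comparison reflects the data-cleaning rule. Unblinded examiners in single-arm teams make that possible, and nothing planned would reveal it.

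**Working it through.** **Plan's own figures.** None is stated for this rule. The nearest benchmark is the 10-point arrest margin (7.1, 7.2), whose sample size reproduces: (1.645 + 0.842)² × 2 × 0.20 × 0.80 / 0.10² gives 198 per group at one-sided 5% and 80% power. The design effect is 1 + (235 − 1) × 0.10 = 24.4, and 396 × 24.4 = 9,662.

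**Step 1: chance that a visit is lost.** Let k be the number of teeth recorded decayed at the prior visit, and r the probability per such tooth of a reversal that stays unresolved after hand check. Both are assumptions. With independence between teeth, P(lost) = 1 − (1 − r)^k.

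| r | k = 0 | k = 1 | k = 3 | k = 5 | k = 10 |
|---|---|---|---|---|---|
| 2% | 0% | 2.0% | 5.9% | 9.6% | 18.3% |
| 5% | 0% | 5.0% | 14.3% | 22.6% | 40.1% |

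The zero at k = 0 and the rise with k hold for any r above zero. The levels depend on r.

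**Step 2: which visits go.** Take 40% of children with decay (the baseline prevalence in 7.1) and, as an assumption, a geometric k among them with mean 2.5, cut at 20. The share of their visits kept is 0.4(1 − r) / [1 − 0.6(1 − r)]. At r = 5% this is 0.38 / 0.43 = 0.884, so 11.6% are lost; at r = 2%, 4.9% are lost; at r = 10%, 21.7%. Lost visits have mean k of 3.92, 3.82 and 3.67 at r = 2%, 5% and 10%, against 2.50 overall. Of visits by children with k of 5 or more, 88%, 72% and 51% are kept. Children with k = 1 supply 16% to 18% of the lost visits.

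**Step 3: effect on estimates.** Further assumptions: no true arm difference; follow-up decay in 10% of children with k = 0 and in 1 − 0.45^k of the others; arrest of 20% on average (the proportion in 7.1), falling 3 points per extra decayed tooth and floored at zero.

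- True prevalence: 0.6 × 0.10 + 0.4 × (1 − 0.18/0.73) = 0.3614.
- Observed at r = 5%: [0.06 + 0.4 × (0.8837 − 0.2300)] / [0.6 + 0.4 × 0.8837] = 0.3215 / 0.9535 = 0.3372. At r = 2% it is 0.3515.
- Equal r in both arms: spurious difference 0, but both arms understate prevalence.
- r = 2% in one arm, 5% in the other: prevalence 0.3515 − 0.3372 = 0.0143 (1.4 points); arrest 0.2056 − 0.2027 = 0.0029 (0.3 points).
- Extreme, 0% against 10%: about 4.7 points in prevalence and 0.9 in arrest.

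The sign reverses if the arms are swapped.

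**The case against.** The strongest reply is that this is ordinary data cleaning with little at stake. Exclusion comes only after a hand check. Charts get weekly quality control (8.15, Table A), out-of-range entries are flagged at entry (8.20), and diagnosis is monitored by site visits and control charts (6.6). A decay-to-sound change may reveal a record attached to the wrong child, in which case dropping the visit is right. It may also mean that the earlier decay call was false, so the flagged child has less disease than recorded. All of this stands. It limits how often the rule bites and leaves the direction of bias open, but it does not alter the dependence on recorded decay or the loss of sound data on other teeth.

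Several stronger readings are tempting and fail:

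- A reader might infer that the rule removes the most diseased children. It removes visits, and in the illustration most visits of heavily affected children remain.
- A reader might infer that only reversals are checked while false new decay passes. Section 8.11 has several triggers unrelated to decay and gives decay-to-sound as an example. A sound-to-decay change is the outcome event, which no edit check should delete.
- A reader might infer that restored lesions cannot revert to sound whereas lesions treated with silver diamine fluoride can. Temporary fillings may be lost or rescored. Arrested lesions are described as dark and hard (3.2) and are coded separately as arrested decay (6.1.6), which arguably makes them harder to score as sound.
- A reader might infer a conflict with intent to treat. Section 7.3 says "For study outcomes, participants will be analyzed using intent to treat" and explains this as analysis as randomized whatever was received. Losing one visit leaves the child in the assigned arm, so the issue is missing data.

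Setting only the reversed surface to missing is still selection on the outcome, on a smaller scale. That is why the fix also needs an analysis on the values as recorded.

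**Conclusion.** The point holds as a cheap improvement. From the text alone, the whole-visit exclusion for an unresolved decay-to-sound change depends on previously recorded decay, discards usable data on other teeth, and has no reporting by arm or sensitivity analysis. A difference between arms is possible because of unblinded, single-arm teams; it is not shown.

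Size and direction cannot be determined from the documents. In the illustration, moderate differences in flag rates shift arrest by 0.3 points and prevalence by 1.4, and the extreme case by 0.9 and 4.7. The arrest figures are small against the 10-point margin; 7.2 states no separate margin for prevention. These figures rest on assumed reversal rates, an assumed distribution of decayed teeth, independence between teeth and assumed links to outcome. They show that the mechanism works and do not estimate its effect in this trial.

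**What to change.** Amend 8.11 to separate two cases. Keep exclusion of the whole visit for unresolved identifier, demographic or other record-mismatch errors. For an isolated decay-to-sound change that the hand check cannot resolve, set only the affected tooth or surface to missing and keep the rest of the visit, in line with the tooth-level handling already in 7.2. Report the number of these exclusions by arm. Add one sensitivity analysis that uses the recorded values as they stand.

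The cost is a short change to 8.11, one table row by arm and one extra analysis. The downside is that a few noisy records are retained.
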